9.2.1.1 Primary efficacy analysis

The primary efficacy endpoint is the proportion of subjects achieving a platelet count of $\geq 100 \times 10^9/L$ on Procedure Day, when measured prior to a platelet transfusion (if any). Subjects with missing information due to early withdrawal or other reasons are considered as having a platelet count $< 100 \times 10^9/L$ in the analysis; that is, missing values are considered as non-responders. The primary endpoint will be estimated from a binomial distribution, with 95% confidence interval (CI) of the proportion calculated. The study will be claimed successful if the lower boundary of the 2-sided 95% CI is above the 0.65. The primary analysis will be performed on the FAS and repeated on the PPS.

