2 STUDY OBJECTIVES

2.1 Primary Objective

The primary objective of this study is to evaluate the efficacy of avatrombopag in increasing platelet counts in subjects with thrombocytopenia scheduled for operations to critical sites or operations with a high risk of bleeding.

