5.2 Rationale for Dosing

A PK/PD model was developed to simulate platelet response to avatrombopag administration in order to select a dose regimen for this study. Using data from healthy volunteers and patients with chronic liver disease, the PK/PD model evaluated the relationship of avatrombopag concentrations to increases in platelet counts. Simulations were performed assuming the baseline platelet count ranged between 50 and $<100 \times 10^9/L$ with a requirement to increase the platelet count to levels $\geq 100 \times 10^9/L$ prior to the procedure. Simulations suggested that 60 mg avatrombopag administered once daily for 5 days with the procedure scheduled 5 to 8 days after the last dose of study drug would result in approximately 85% of subjects having platelet counts that exceed $100 \times 10^9/L$. Simulations were also performed for subjects with CLD. In order to limit the number of subjects with a platelet count $>200 \times 10^9/L$ after treatment yet still have the majority of subjects with a platelet count $\geq 100 \times 10^9/L$ on the day of surgery, subjects with CLD must have a platelet count between 50 and $<75 \times 10^9/L$ at Baseline.

To ensure the accuracy of the predictions, platelet response data will be reviewed by the Sponsor and Medical Monitor, and if necessary, the Investigators participating in the study, after the enrollment of 25% and 50% of subjects to determine if the dose for subsequent subjects enrolled in the study should be increased to 80 mg once daily for 5 days.

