6.4 Visit 4 - Procedure Day

The following procedures will be performed pre-operatively on Procedure Day at Visit 4 (Day 10 [+3 days]):

- Record vital signs (includes weight, body temperature, blood pressure, and pulse rate);
- Collect blood samples for the following assessments:
 - Hematology (central laboratory only),
 - Platelet count (local and central laboratories),
 - Coagulation (central laboratory only), and
 - Serum chemistry (central laboratory only);
- Record whether subject required a platelet transfusion;
- If any bleeding, perform ISTH non-surgical bleeding assessment (see Appendix D);
- Contact IRT; and
- Collect study drug package and any unused study drug.

The following procedures will be performed post-operatively on Procedure Day at Visit 4 (Day 10 [+3 days]):

- Record concomitant medications,
- Record adverse events,
- Record whether subject required any rescue procedure for bleeding, and
- If any bleeding, perform ISTH surgical bleeding assessment (see Appendix D).

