9.2.4 Sample Size Determination

It is estimated from PK/PD modeling that the proportion of subjects treated with avatrombopag expected to achieve a platelet count of $\geq 100 \times 10^9/L$ on Procedure Day, when measured prior to platelet transfusion (if any), is approximately 85%. Assuming the true response rate is 0.8 and the desired lower boundary of the 2-sided 95% CI is at least 0.65, 60 enrolled subjects will provide greater than 90% power. If the decision is made to increase the dose of study drug at one of the interim reviews of the data based on the pre-defined boundaries, up to an additional 30 subjects may be enrolled in the study for a maximum sample size of 90 subjects.

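### A dosed subject whose operation is cancelled before the Visit 4 draw is scored as a platelet failure, because the protocol does not ensure a Day 10 to 13 count

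*Protocol*

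**What the plan says.** - **Objective.** Protocol 2.1 sets out to "evaluate the efficacy of avatrombopag in increasing platelet counts". Whether the operation takes place is not part of that aim.
- **Deciding sample.** Sections 7 and 9.2.1.1 define response by the count on Procedure Day, before any platelet transfusion. Section 6.4 places the draw before surgery: "The following procedures will be performed pre-operatively on Procedure Day at Visit 4", with a window of Day 10 (+3 days).
- **Neighbouring counts.** Visit 3 is at Day 5 (-2 days; 6.3.1). Visit 5 is timed from the procedure (6.5.1). Visit 6 is at Day 35 (±3 days; 6.5.2).
- **Denominator.** The Full Analysis Set is every enrolled subject who took at least one dose (9.1). Replacement is allowed only for withdrawal before dosing (4.3).
- **Missing counts.** Section 9.2.1.1: "Subjects with missing information due to early withdrawal or other reasons are considered as having a platelet count" under 100 × 10⁹/L, that is, as non-responders.
- **Decision rule.** "The study will be claimed successful if the lower boundary of the 2-sided 95% CI is above the 0.65".
- **Planning.** Section 9.2.4 plans on a true rate of 0.80 against the 0.65 bound and states that "60 enrolled subjects will provide greater than 90% power". No allowance for missing counts is stated. The model in section 5.2 assumes "the procedure scheduled 5 to 8 days after the last dose of study drug". On that timing it predicts a count above 100 × 10⁹/L in about 85% of subjects.

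**The concern.** Elective operations are sometimes called off for reasons that have nothing to do with platelets, such as an infection or a scheduling problem. If that happens after dosing but before the Visit 4 draw, the protocol does not tell the site to take a Day 10 to 13 platelet sample. If none is taken, the subject is a failure by rule, whatever the drug did.

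The trial has one arm and a fixed threshold of 0.65, so each such subject lowers the estimate directly, with no control arm to share the loss. A statistical analysis plan written later could change how a missing count is handled, but it could not recover a sample that was never drawn. The point therefore belongs in the protocol.

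**Working it through.** **1. What happens to a dosed subject whose operation is cancelled before the draw**

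| Step | Source | Consequence |
|---|---|---|
| Dosed | 9.1 | in the Full Analysis Set |
| Replacement | 4.3 | not available after dosing |
| Visit 4 count | 6.4, Table 1 | tied to Procedure Day; no instruction if there is no operation |
| Visit 5 count | 6.5.1 | timed from the procedure, so it has no date |
| Next count on a fixed study day | 6.5.2 | Day 35, far outside the response window |
| Missing count | 9.2.1.1 | non-responder |

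An early termination visit (6.6) includes a platelet count, but it has no fixed day and 9.2.1.1 does not let it stand in for the Procedure Day count.

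With the last dose on Day 5, the modelled window of 5 to 8 days after the last dose is Day 10 to Day 13. That is the window Visit 4 already has, so a count taken then is the quantity that the 85% prediction describes.

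**2. Responders needed for success**

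n = 60 and the lower limit of the 2-sided 95% interval must exceed 0.65. Section 9.2.1.1 does not name the interval method, so two are shown.

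- Exact (Clopper-Pearson): lower limit 0.640 at 46/60 and 0.658 at 47/60, so 47 are needed. Wilson also needs 47.
- Wald: 45/60 gives 0.75 − 1.96 × √(0.75 × 0.25/60) = 0.640. 46/60 gives 0.767 − 1.96 × √(0.767 × 0.233/60) = 0.660. So 46 are needed.

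**3. The protocol's own figure**

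At a true rate of 0.80 the stated power above 90% does not reproduce: P(X ≥ 47) = 69.4% (exact rule) and P(X ≥ 46) = 79.3% (Wald rule). At 0.85 the figures are 94.2% and 97.1%. This shortfall at 0.80 exists with no cancellations at all. It is a separate error and is not counted here. Both true rates are carried forward.

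**4. Effect of lost counts**

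Let m be the share of dosed subjects with no count because of cancellation, unrelated to response. The observed response rate is then p × (1 − m), and power is P(X ≥ r) for a binomial with n = 60 and that rate. The values of m are assumptions.

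| True p | m | p(1 − m) | Exact rule, r = 47 | Wald rule, r = 46 |
|---|---|---|---|---|
| 0.85 | 0 | 0.850 | 94.2% | 97.1% |
| 0.85 | 2% | 0.833 | 88.3% | 93.4% |
| 0.85 | 5% | 0.8075 | 74.5% | 83.4% |
| 0.80 | 0 | 0.800 | 69.4% | 79.3% |
| 0.80 | 2% | 0.784 | 57.9% | 69.3% |
| 0.80 | 5% | 0.760 | 40.3% | 52.3% |

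Five per cent of 60 is three subjects. Exactly one lost count means that 47 responders must come from the other 59: P(X ≥ 47) with n = 59 is 90.4% at 0.85 and 60.2% at 0.80.

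**5. If some operations are cancelled because the count is low**

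Those subjects are failures with or without a sample. Suppose 5% are cancelled and half of these for a low count. Only 2.5% are then lost for unrelated reasons. The observed rate is 0.85 × 0.975 = 0.829 or 0.80 × 0.975 = 0.78, and exact power is 86.4% or 54.9%, against 74.5% or 40.3% when all 5% are unrelated.

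**The case against.** **The protocol is silent, not explicit.** A reader might infer that the primary count exists only if the operation takes place. The text does not say so. The draw is pre-operative and Visit 4 has a calendar window, so an operation called off after the draw leaves a usable sample, and a site could hold Visit 4 without surgery. This stands. What remains is that nothing requires the draw, and sites may act differently.

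**Postponement.** A reader might also infer that postponed operations damage the endpoint. A move within Day 10 to 13 stays inside the modelled window. Surgery after Day 13 departs from the protocol's schedule, and handling of such counts can be left to the analysis plan. Substituting a Day 10 to 13 count there would change the question from the count at surgery to an earlier count, and could favour the drug: a subject above 100 on Day 12 but below it at a later operation would become a responder. Postponement is therefore not part of this point.

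**The size rests on assumed rates.** This is true. The fall from 0.85 in the model to 0.80 in the sample-size text is unexplained. It would cover 1 − 0.80/0.85 = 5.9% of lost counts if it was meant as an allowance, and applying losses to 0.80 would then discount twice. The protocol does not say this, so both starting rates are shown.

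**Missing as failure is a deliberate safeguard.** In an open-label, single-arm trial it protects against false success, and that is a good reason to keep it where no count exists. It is not a reason to leave a sample undrawn. The per-protocol repeat does not solve the problem, because it is only a sensitivity analysis (9.2.1).

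**Conclusion.** The point holds in a limited form. The protocol does not ensure a Day 10 to 13 platelet count for a dosed subject whose operation is cancelled before the Visit 4 draw, and it scores that subject as a non-responder when no count is taken. The bias is towards false failure only.

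If cancellation is unrelated to response, 2% to 5% lost counts cost about 6 to 20 percentage points of power under the exact rule at a true rate of 0.85, and about 12 to 29 points at 0.80. Under the Wald rule the ranges are about 4 to 14 and 10 to 27 points. These figures depend on cancellation rates that the protocol does not give, and they shrink if some operations are cancelled because of a low count. A reader might infer that the trial is bound to lose much of its power this way; the documents do not support that, because the cancellation rate is unknown. Nor should the gap between the stated power above 90% and 69.4% at 0.80 be attributed to this cause.

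The change is worth making because it is cheap, has to be made before the samples are due, and is neutral in the case most open to suspicion: a subject cancelled for a low count who is still below 100 × 10⁹/L at the draw remains a failure.

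**What to change.** - **Section 6.4 and Table 1:** state that the Visit 4 platelet sample is drawn on Day 10 (+3 days), before any platelet transfusion, even if the operation has been cancelled.
- **Sections 7 and 9.2.1.1:** use that count for the primary endpoint when the operation does not take place. Keep missing as non-responder only where no such count exists.
- **Sensitivity analysis:** report the rule as now written, with every cancelled operation that has no Procedure Day count scored as a non-responder.
- **Operations that go ahead, including postponed ones:** leave the Procedure Day count as the endpoint, and list separately those done after Day 13.

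The cost is protocol wording, one already scheduled blood draw in the subjects whose operation is cancelled, and a slightly wider endpoint definition. No dose or clinical rule changes.

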9.2.1.2 Secondary efficacy analysis

The following secondary efficacy endpoints will be summarized and analyzed in the same manner as the primary efficacy endpoint:

- Proportion of subjects without platelet transfusion and any other treatment for bleeding after the Baseline Visit and up to 7 days following Procedure Day,
- Proportion of subjects without platelet transfusion after the Baseline Visit and up to 7 days following Procedure Day, and
- Proportion of subjects without bleeding after the Baseline Visit and up to 7 days following Procedure Day.

Change in platelet count from baseline to Procedure Day for avatrombopag will be calculated for each subject and summarized descriptively. The mean (95% CI) and median (range) will be provided.

9.2.1.3 Other efficacy analysis

Additional efficacy analyses will be performed if deemed necessary. The details of the analyses will be described in the Statistical Analysis Plan that will be finalized prior to database lock.

9.2.2 Analysis of Safety

Safety and tolerability will be assessed by examining the incidence of adverse events, physical examination findings, clinical laboratory parameters, and vital signs over time using the Safety Analysis Set.

9.2.3 Interim Analysis

Two interim data reviews are planned to assess study design assumptions and adjust study drug dose regimen if necessary.

The first interim data review will be conducted when approximately 25% of subjects (approximately 15 subjects) have been enrolled. For the primary efficacy endpoint, if fewer than 10 responders out of 15 enrolled subjects are observed (the probability of observing <10 responders out of 15 enrolled subjects is 0.0611 if the true response rate is 0.8), the avatrombopag dose increase (to 80 mg) will be considered for the subsequent enrolled subjects. Otherwise, the study will continue as planned until the second interim data review.

In the event that the avatrombopag dose was not adjusted after the first interim data review, the second interim data review will be conducted when approximately 50% of subjects (approximately 30 subjects) have been enrolled. If fewer than 21 responders out of 30 enrolled subjects are observed (the probability of observing <21 responders out of 30 enrolled subjects is 0.0611 if the true response rate is 0.8), the avatrombopag dose increase (to 80 mg) will be considered for the subsequent enrolled subjects. Otherwise, the study will continue as planned until the completion of the study.

Details of the planned interim analyses will be provided in the Interim Analysis Plan.

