Subjects will receive 60 mg oral avatrombopag once daily for 5 days beginning on Day 1, followed by a wait period prior to the procedure, which will occur on Day 10 (+3 days). The platelet response data will be reviewed after approximately 25% and 50% of subjects have been enrolled in the study. If required, the dose may be adjusted for subsequent subjects based on insufficient increase in platelet counts on Procedure Day. If a higher dose is considered necessary, subjects will receive 80 mg oral avatrombopag once daily for 5 days beginning on Day 1, followed by a wait period prior to the procedure, which will occur on Day 10 (+3 days).

The Follow-up Period will include 2 visits, which will occur at approximately 7 days (+3 days) post-procedure and 30 days (± 3 days) after the last dose of study drug.

The total study duration will be approximately 5 to 7 weeks.

DOSAGE FORMS AND ROUTE OF ADMINISTRATION:

Subjects will receive 60 mg oral avatrombopag once daily for 5 days. If required, the dose may be adjusted for subsequent subjects based on insufficient increase in platelet counts on Procedure Day. If a higher dose is considered necessary, subjects will receive 80 mg oral avatrombopag once daily for 5 days.

EFFICACY VARIABLES:

The primary efficacy endpoint is the proportion of subjects achieving a platelet count of $\geq 100 \times 10^9/L$ on Procedure Day, when measured prior to a platelet transfusion (if any).

The secondary efficacy endpoints include the following:

- Change in platelet count from baseline to Procedure Day,
 - Proportion of subjects without platelet transfusion and any other treatment for bleeding after the Baseline Visit and up to 7 days following Procedure Day,
 - Proportion of subjects without platelet transfusion after the Baseline Visit and up to 7 days following Procedure Day, and
 - Proportion of subjects without bleeding after the Baseline Visit and up to 7 days following Procedure Day.
-

SAFETY VARIABLES:

Safety variables will include adverse events, physical examination findings, clinical laboratory parameters, and vital signs.

STATISTICAL ANALYSES:

Efficacy Analysis

All primary and secondary efficacy endpoints will be analyzed using the Full Analysis Set (FAS). The Per-Protocol Analysis Set (PPS) will be used only for sensitivity analysis of the primary and secondary efficacy endpoints.

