4.3 Withdrawal Criteria

Participation of a subject in this clinical study may be discontinued for any of the following reasons:

- The subject withdraws consent or requests discontinuation from the study for any reason;
- Occurrence of any medical condition or circumstance that exposes the subject to substantial risk and/or does not allow the subject to adhere to the requirements of the protocol;
- Any SAE, clinically significant adverse event, severe laboratory abnormality, intercurrent illness, or other medical condition which indicates to the Investigator that continued participation is not in the best interest of the subject;
- Pregnancy;
- Requirement of prohibited concomitant medication;
- Subject failure to comply with protocol requirements or study-related procedures; or
- Termination of the study by the Sponsor or the regulatory authority.

If a subject withdraws prematurely from the study due to the above criteria or any other reason, study staff should make every effort to complete the full panel of assessments scheduled for the Visit 6 (Day 35 [± 3 days]). The reason for subject withdrawal must be documented in the electronic case report form (eCRF).

In the case of subjects lost to follow-up, attempts to contact the subject must be made and documented in the subject's medical records.

Subjects withdrawn prior to receiving a dose of study drug may be replaced as needed to meet the enrollment objectives of the study.

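### Do the enrolment-based interim reviews undermine the stated 0.0611 chance of crossing each boundary?

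*Protocol*

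**What the plan says.** Protocol section 9.2.3 sets the first review by enrolment: "The first interim data review will be conducted when approximately 25% of subjects (approximately 15 subjects) have been enrolled". The second, held if the dose was not changed at the first, comes at about 30 enrolled. The Synopsis (Study Design and Duration) and section 3.1 say the same in general terms: "The platelet response data will be reviewed after approximately 25% and 50% of subjects have been enrolled in the study". Section 5.2 places the reviews "after the enrollment of 25% and 50% of subjects".

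The boundaries in section 9.2.3 concern the primary efficacy endpoint. A dose increase will be considered "if fewer than 10 responders out of 15 enrolled subjects are observed" at the first review. The second boundary reads: "If fewer than 21 responders out of 30 enrolled subjects are observed". Each carries a crossing probability of 0.0611 at a true response rate of 0.8. The section ends: "Details of the planned interim analyses will be provided in the Interim Analysis Plan".

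The endpoint is a platelet count on Procedure Day, which sections 3.1 and 6.4 put at Day 10 (+3 days). Section 9.2.1.1 counts missing values as non-responders in the primary analysis. Section 9.1 limits the Full Analysis Set to enrolled subjects who took at least one dose, and section 4.3 adds: "Subjects withdrawn prior to receiving a dose of study drug may be replaced as needed to meet the enrollment objectives of the study".

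**The concern.** Enrolment and outcome are 9 to 12 days apart (Day 1 to Day 10, or Day 13 at the end of the window). On the day the 15th or 30th subject enrols, at least that subject cannot be classified. A probability computed for 15 or 30 known outcomes then seems not to describe a review held at that moment. If a pending subject cannot count as a responder, the boundary is easier to cross than stated.

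The denominator also looks loose. Section 9.2.3 counts enrolled subjects, the primary analysis counts dosed subjects, and those who leave before dosing may be replaced.

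At stake is how often a review would prompt consideration of a dose increase when the true rate is already 0.8. Section 9.2.4 allows up to 30 further subjects if the increase is decided on. The 0.0611 is the only operating characteristic the protocol gives for either boundary.

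**Working it through.** **Inputs.** Section 9.2.3: boundaries of fewer than 10 of 15 and fewer than 21 of 30, true rate 0.8, stated probability 0.0611 for each. Sections 3.1 and 6.4: outcome on Day 10 (+3 days). The number of pending subjects is not in the protocol; one is the smallest possible on the day the milestone is reached.

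**The plan's own figures.** With X responders among n subjects, X binomial with rate 0.8:

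- P(X ≤ 9 | n = 15) = 0.06105
- P(X ≤ 20 | n = 30) = 0.06109

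Both round to 0.0611, so the figures are right when all outcomes are known.

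**One subject pending, boundary applied at once, pending subject not a responder.**

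- P(X ≤ 9 | n = 14) = 0.1298
- P(X ≤ 20 | n = 29) = 0.1084

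These are 0.1298/0.0611 = 2.1 and 0.1084/0.0611 = 1.8 times the stated value. Leaving the pending subject out and keeping the cut in proportion gives the same result. At the first review 9/14 = 0.643 lies below 10/15 = 0.667 and 10/14 = 0.714 does not. At the second, 20/29 = 0.690 lies below 21/30 = 0.700 and 21/29 = 0.724 does not.

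**One subject pending, review waits when that subject decides the result.** Among 14 known outcomes, 8 or fewer responders cross the boundary whatever the 15th shows, and 10 or more do not cross. Only exactly 9 of 14 is undecided, and it then crosses only if the 15th subject fails, with probability 0.2. The second review works the same way, with exactly 20 of 29 undecided.

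- First: P(X ≤ 8 | 14) + 0.2 × P(X = 9 | 14) = 0.0439 + 0.2 × 0.0860 = 0.0611
- Second: P(X ≤ 19 | 29) + 0.2 × P(X = 20 | 29) = 0.0493 + 0.2 × 0.0591 = 0.0611

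The whole excess in 0.130 and 0.108 therefore comes from acting on an undecided result instead of waiting at most 12 days for it.

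**Withdrawals.** If 0.8 applied only to subjects who reach Procedure Day, and withdrawals counted as non-responders, assumed withdrawal of 2%, 5% or 10% would lower the rate to 0.784, 0.76 or 0.72. The crossing probabilities would be 0.084, 0.127 or 0.222 at the first review and 0.094, 0.162 or 0.319 at the second. The protocol gives no withdrawal rate, and its wording does not support this reading of 0.8. Section 9.2.1.1 already counts missing values as non-response for this endpoint, section 9.2.3 applies the boundary to the same endpoint, and section 9.2.4 assumes 0.8 where modelling suggested about 85%.

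**Enrolled against dosed.** Section 6.2.2 places the eligibility assessment and the first dose at the same visit, on Day 1. Few subjects could be enrolled without being dosed, and section 4.3 allows for replacing them.

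**The case for a change.** The best case for a change is that the protocol is not silent here. It fixes the trigger, the boundary, the denominator and the probability itself, and section 9.2.3 says the review is held when the subjects have been enrolled. Read literally, the review takes place with at least one outcome unknown, and 0.130 and 0.108 hold under either obvious way of treating that subject. One sentence would remove the doubt.

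The arithmetic stands, and so does the observation that the data cut is not written down. What does not stand is that the written rule has these probabilities. Section 9.2.3 gives an approximate milestone and then, separately, a rule about responders who are observed. The Synopsis and sections 3.1 and 5.2 put the review after the milestone, and the Synopsis and section 3.1 tie any adjustment to platelet counts on Procedure Day. Nothing tells the reviewers to score a pending subject as a failure or to drop that subject and rescale the cut. The non-responder rule in section 9.2.1.1 is written for the primary analysis and for information lost through withdrawal or other causes; it does not mention subjects still waiting for their procedure at an interim review.

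**Conclusion.** No change to the plan is needed. With enrolment read as the approximate milestone and 15 or 30 observed Procedure Day outcomes as the basis of the rule, the trigger, the boundaries and both 0.0611 figures agree. The 0.130 and 0.108 illustrate a scoring rule the protocol does not state, and the withdrawal figures rest on assumed rates and a reading of 0.8 that section 9.2.1.1 does not support.

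What is left is an unstated data cut. Such a detail belongs in the Interim Analysis Plan to which section 9.2.3 refers. That plan is not available here, so whether it sets the cut cannot be confirmed. Even if it did not, the study is open-label and the reviewers can see which outcomes are outstanding. Crossing a boundary leads only to consideration of a dose increase. Spelling out the cut would leave the boundaries, doses, stated probabilities, primary estimate and success criterion as they are. The conclusion rests on the reviewers waiting for an outcome that could decide the result, a delay of at most 12 days after the last subject's Day 1.
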